Appendix S – Glioma History

Study Number: _____ PID: _____

Investigator: [name]. Date: ____ / ____ / ____

Oncologic history

- a) Glioma histologic diagnosis
 - a. Astrocytoma
 - b. Oligodendroglioma
 - c. Glioblastoma
 - d. Other: _____
- b) WHO Grade of glioma: WHO Grade 2 WHO Grade 3 WHO Grade 4
- c) Molecular data (e.g. IDH, MGMT, 1p19q)

Other Medical Conditions/Diagnoses (list all): _____

Molecular Features of the Primary Brain Tumor:

MGMT promoter methylation status	 Methylated  Not methylated  Not reported
IDH mutational status	 IDH1 mutated  IDH2 mutated  IDH1 and IDH2 wild type  IDH1 and IDH2 testing not reported
1p/19q deletion status	 1p19q codeleted  1p deletion only  19q deletion only  1p19q NOT codeleted (normal)  1p and 19q deletion not reported

Treatment Summary:

Treatment	Completed:	Date of Treatment(s)	Notes
Radiation	Yes  No 		

Therapy		RT start date: ____/____/____ RT end date: ____/____/____	
Concurrent Chemotherapy	Yes  No 	Name of chemotherapy: _____	
Adjuvant Chemotherapy	Yes  No 	Name of chemotherapy: _____	

Recurrence Information:

Recurrence Number	Recurrence (y/n): Yes  No 	Date of Recurrence ____/____/____	Treatment
First Recurrence	Yes  No 	____/____/____	
Second Recurrence	Yes  No 	____/____/____	
Third Recurrence	Yes  No 	____/____/____	
Fourth Recurrence	Yes  No 	____/____/____	
Fifth Recurrence	Yes  No 	____/____/____	

Appendix T – Telephone Script

Study Number: _____ PID: _____

Investigator: [name]. Date: ____/____/____

Hello, my name is {TBD - Project Coordinator} and I am calling on behalf of {Wake Forest Baptist Medical Center}. May I please speak with {SUBJECT'S NAME}?

I am going to ask you several questions about any side effects that you have experienced in the last week. When answering these questions, I would like for you to think only about symptoms that you have had over the last 1 week. We will focus on the period of time that you have been on the current dose of the solriamfetol drug that is a part of this study.

Over the last 1 week, have you had any side effects from solriamfetol (the study drug)? Yes No

Over the last 1 week, have you had any of the following symptoms (and if so, please describe them)?

- Headache _____
- Nausea _____
- Decreased appetite _____
- Anxiety _____
- Diarrhea _____
- Dry mouth _____
- Insomnia _____
- Chest pain _____
- New shortness of breath _____
- Other _____

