Safety is an important first step and study outcome. In the published phase 2 and 3 studies of solriamfetol in patients with narcolepsy or obstructive sleep apnea (OSA), adverse events included headache (9-16%), nausea (12-14%), diarrhea (11%), decreased appetite (6-14%), anxiety (6-11%), chest discomfort (9%), insomnia (6%), muscle tightness (6%), nasopharyngitis (5-14%), and dry mouth (5-10%). Cancer patients and in particular brain tumor patients are at risk for some of these and other cognitive, seizure, or neurological toxicities that need to be explored at each of solriamfetol's three dose levels (75 mg, 150 mg, 300 mg) prior to proceeding to a primary efficacy endpoint. The current trial will establish this experience.

Prior studies of solriamfetol have shown early improvements in patient-reported sleep by ESS scores. In the current study we will also evaluate other associated symptoms of fatigue, neurocognition, mood, and quality of life. It is not clear that these associated symptoms will respond as quickly to drug therapy. In fact, according to our model of the sleep-fatigue-neurocognitive symptom cluster (Figure 1), we suspect that improvement in fatigue, neurocognition, mood and quality of life are downstream of the improvement in sleep and thus, in this study, endpoints will be assessed after prolonged stable drug therapy. This should not affect the ability to assess for improvements in sleep which have been reported as early as 1 week after solriamfetol treatment and remained stable over up to 12 weeks of continued treatment in the aforementioned studies.

2 Hypotheses

1. Primary Hypothesis

We hypothesize that the side effect profile of solriamfetol at doses of 75 mg daily, 150 mg daily, and 300 mg daily will be similar in patients with primary brain tumors to that reported in patients with narcolepsy and obstructive sleep apnea.

Serious adverse events in patients with primary brain tumors including significant confusion/ altered mental status, seizures, or other side effects will not be more common at the 300 mg daily dose compared to the 150 mg and 75 mg daily doses.

2. Secondary Hypotheses

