Pittsburgh Sleep Quality Index (PSQI)		X				X	X	
Associated Symptom PROMs: BFI, CFS, BDI		X				X	X	
QOL PROMs: FACT-Br		X				X	X	
Neuro-cognitive Battery		X					X	
Standard of Care MR Brain ^a	X						X ^j	

¹ Patient's undergoing telehealth assessment at the pre-screening timepoint require virtual examination by observation only. Blood draw and laboratory testing can be performed locally and reviewed remotely.

^a Pre-study requirements listed in table must be completed **within** 21 days prior to registration.

^b Blood pressure (mmHg), heart rate (BPM)

^c Height, Weight, M² Patients undergoing telehealth assessment can provide this information verbally using home device (e.g. scale).

^d Albumin, alkaline phosphatase, total bilirubin, bicarbonate, BUN, calcium, chloride, creatinine, glucose, potassium, total protein, SGOT[AST], SGPT[ALT], sodium.

^e Serum pregnancy test (women of childbearing potential).

^f May be performed by telephone.

^g Epworth Sleepiness Scale (ESS) will be completed either in the clinic (D1, D29, D70) at each of the study visits (V1, V2, V3) or by telephone (D8, D15, D22) during the flexible dose escalation portion of the study.

^h 7-day sleep diary is to be completed at baseline (D1-7), continuously during dose escalation (D8-14, D15-21, D22-28), and during the first and last week of fixed dose drug continuation (~D29-35 and ~D63-70). Actigraphy will be collected continuously.

ⁱ Patients may complete the baseline sleep diary and actigraphy prior to the Baseline Visit (V1) or after the Baseline Visit (V1).

^j Post-treatment MR Brain is to be performed D85 \pm 42 days.

^k Study visits may be conducted via telehealth visit. Blood draw and EKG (when appropriate) can be performed locally and reviewed remotely.

3. Screening

Glioma patients seen at the Wake Forest Baptist Medical Center will be considered for eligibility at or before their scheduled visits. In general, patients may be approached at the time of routine outpatient visit for follow up with neuro-oncology, medical oncology, radiation oncology, and neurosurgery.

Patients who are identified as potential study candidates will have an opportunity to hear about the study and complete written informed consent. Patients who sign informed consent and do not meet eligibility criteria will be considered screen failures, will not be evaluable for the primary endpoint, will not count toward the total sample size, and this enrollment will be replaced.

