Adverse events will be assessed by telephone call completed on D8+1 day, D15+1 day, and D22+1 day. Patients will be assessed in clinic at D29+7 days. Patients who report a symptomatic dose-limiting toxicity will de-escalate treatment back to the highest previously tolerated dose and will be seen for V2.

6. Fixed Dose Drug Continuation

At the completion of the flexible dose titration, patients will be seen for a routine study visit (V2) or via telehealth visit to document adverse events at the completion of flexible dosing, review sleep diary and actigraphy, and complete V2 assessments. Data from this interim time point may be used to clarify the trajectory of improvement, decline, and no change in study assessments. Patients will then proceed with fixed dose treatment at 300 mg p.o. once daily or the maximum tolerated dose for that patient.

Fixed dose drug continuation will be continued for 6 weeks. Patients will complete a sleep diary for the first 7 and last 7 days of fixed dose treatment; actigraphy will be collected continuously. At the completion of fixed dose treatment, patients will be seen for V3 study assessments (Section 6.7).

7. 30 Day Follow Up

All patients will be followed for 30 days following the completion of treatment to assess for delayed toxicity. Adverse events will be recorded at this 30 day follow up visit. If the patient is unable to return for this visit, adverse events will be recorded by telephone or telehealth visit.

8. Study Assessments

Assessment of sleep, neuro-cognitive function, fatigue, mood and quality of life will be assessed at baseline (V1) and at the end of the fixed-dose drug continuation phase of the study (V3). Given that patient drop out could occur during the course of the study treatment, study assessments that are not subject to significant practice and/or repeated measure effects will also be assessed after the flexible dose titration period (V2).

The following assessments will be performed:

1. Patient-reported outcome measures (PROMs) for sleep:

Changes in patient-reported outcomes measures (PROMs) are pivotal to cancer control drug approval.

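### The telephone adverse-event script does not ask about seizures or confusion, and how these events are solicited differs by dose

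*Combined protocol and SAP*

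**What the plan says.** **The events of interest.** Section 2.1 states that serious adverse events "including significant confusion/ altered mental status, seizures, or other side effects will not be more common at the 300 mg daily dose" than at 150 mg and 75 mg. The study rationale (section 1.6) says that brain tumor patients are at risk of "cognitive, seizure, or neurological toxicities that need to be explored at each of" the three dose levels before an efficacy study. The primary outcome (section 6.1) is wider than serious events: it is adverse events graded by CTCAE v5.0. Section 13.1 tabulates their severity and frequency for each dose and compares the doses by chi-squared or Fisher's exact test.

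**The script.** Appendix T opens with "Over the last 1 week, have you had any side effects from solriamfetol (the study drug" and then asks "Over the last 1 week, have you had any of the following symptoms (and if so, please describe them". The list is headache, nausea, decreased appetite, anxiety, diarrhea, dry mouth, insomnia, chest pain, new shortness of breath and 'Other'.

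**The contacts.** Section 7.5 says "Adverse events will be assessed by telephone call completed on D8+1 day, D15+1 day, and D22+1 day" and then "Patients will be assessed in clinic at D29+7 days". The D29 contact is V2. It carries footnote k of the schedule in section 7.2, which says "Study visits may be conducted via telehealth visit". V2 includes a physical exam and FACT-Br. FACT-Br is given at V1, V2 and V3 only (section 7.8), and its item Br2 (Appendix N) concerns seizures in the past 7 days. In the six-week fixed-dose phase, section 7.1 schedules adverse-event assessment once, at the end.

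**The concern.** The first seven script items are the common adverse events from the narcolepsy and sleep apnea trials, in the order given in section 10.1. The script thus asks about the risks seen in earlier populations and leaves out the two that the hypothesis names for glioma.

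Two things are at stake. The first is detection. The calls are the scheduled checks before each dose increase, and section 7.9.1 counts some neurological toxicities among the dose-limiting ones. A breakthrough seizure handled by a minor antiepileptic change is not dose-limiting under that section and may never reach a hospital. It is still an adverse event under the primary outcome.

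The second is comparability. If the same event is solicited differently at different doses, part of any difference in the section 13.1 comparison may come from the method of asking.

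**Working it through.** The plan gives no figure on this point, so the check sets the passages side by side. An illustration follows.

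**1. What is asked, and when** (section 7.2 schedule, sections 7.1, 7.5 and 7.8, Appendices D, F, G, N and T)

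| Period | Scheduled contact | Direct seizure question | Direct confusion question | Other routes |
|---|---|---|---|---|
| 75 mg week | Call, D15 | None | None | Open question, 'Other' line, daily diary, serious-event reporting |
| 150 mg week | Call, D22 | None | None | As above |
| 300 mg titration week | V2, D29, clinic or telehealth | FACT-Br Br2 | None as such; FACT-Br asks about concentration and putting thoughts together | Daily diary, serious-event reporting; no visit checklist shown |
| Fixed dose, six weeks | V3, one contact | FACT-Br Br2, last 7 days only | As at V2 | Daily diary, serious-event reporting |

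Within titration, a direct seizure question is scheduled after 300 mg and not after 75 or 150 mg. Contact mode and solicitation therefore move together with dose.

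**2. What the remaining routes ask of the patient.** The open question asks for effects of the drug, so the patient must first attribute the event. Section 7.3 expects about 60% of patients to be prescribed an antiepileptic, and such a patient may put a seizure down to the tumor. The 'Other' line and the diary column depend on the event being volunteered. The script asks to speak with the subject and has no caregiver question. That confusion is poorly suited to unprompted self-report is a judgment, not something the documents state.

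**3. Illustration of size.** Assumptions: equal true risk p at every dose, capture s at 75 and 150 mg, and full capture at 300 mg. The documents give no value for s or p. The numbers treated, 36, 33 and 30, are the planning figures in section 13.4.

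- Expected recorded cases: 36·p·s, 33·p·s and 30·p.
- Apparent risk ratio, 300 mg against the lower doses: p/(p·s) = 1/s.
- Chance of a falsely significant excess at 300 mg: exact enumeration of Fisher's test, 30 patients against 36 + 33 = 69, two-sided 0.10. Section 13.1 sets no level for this comparison, so 0.10 is borrowed from section 13.4. The groups are treated as independent, although the same patients contribute to each dose.

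| p = 10%, s | Expected cases 75/150/300 mg | Apparent ratio | Chance of false excess |
|---|---|---|---|
| 1.0 | 3.6 / 3.3 / 3.0 | 1.0 | 4.3% |
| 0.8 | 2.9 / 2.6 / 3.0 | 1.25 | 8.3% |
| 0.5 | 1.8 / 1.7 / 3.0 | 2.0 | 21.7% |
| 0.25 | 0.9 / 0.8 / 3.0 | 4.0 | 45.2% |

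At s = 0.5 the last column is 15.5% for p = 5% and 34.6% for p = 20%.

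**4. The reverse case.** Suppose capture is full at the lower doses and s at 300 mg, because one contact must cover six weeks. The ratio becomes (p·s)/p = s, which is 0.8 at s = 0.8 and 0.5 at s = 0.5. The same arithmetic then hides a true excess at 300 mg.

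**The case against.** The case against rests on five arguments.

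- **The calls are not the only source at the lower doses.** Appendix F gives a daily side-effect column for each titration week. The script has an open question and an 'Other' line. Section 7.6 uses V2 to document adverse events at the completion of flexible dosing, without limiting this to the 300 mg week. This stands.
- **The hypothesis concerns serious events.** Appendix D requires unplanned hospitalization of more than 24 hours to be reported at any grade, whatever the dose, and the seizure criterion for dose-limiting toxicity itself requires hospitalization. This stands for the hypothesis sentence. It does not cover milder events, which section 13.1 also tabulates.
- **Better prompting at 300 mg is not shown.** No V2 adverse-event checklist appears, V2 may be remote, and an exam will usually not reveal a seizure from earlier in the week. Br2 belongs to a quality-of-life instrument that the plan does not name as an adverse-event source. This stands, and it limits what can be said about direction.
- **Callers may ask more than the script.** Nothing restricts them to Appendix T, and only the heading of the Adverse Event Log (Appendix E) can be read in the available text. This is fair, but a written script is what the plan commits to.
- **The study is mainly descriptive** (section 13.4). That lowers the stakes of a false test result. It does not lower the value of detecting these events.

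A reader might infer that seizures and confusion will be undercounted at 75 and 150 mg and that a false dose gradient will follow. The documents do not support that. The other routes operate at the lower doses, and the single contact after six fixed-dose weeks could reduce capture at 300 mg instead.

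**Conclusion.** The point holds as a gap in solicitation. Followed as written, Appendix T does not ask about two events that the primary hypothesis names, at the checks that close the 75 mg and 150 mg weeks. A seizure item is scheduled after the 300 mg week and not after the others. Non-hospitalized seizures and confusion may be missed, and ascertainment may differ between doses.

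Size and direction remain open. The 1.25- to 2-fold range follows entirely from assumed capture of 50% to 80% at the lower doses and full capture at 300 mg. For serious events capture may be close to complete at every dose, and the distortion would then be negligible. If a bias of the illustrated kind exists, it works against the study's own hypothesis by making 300 mg look worse. This is a cheap improvement, not a flaw that undermines the primary analysis.

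**What to change.** Add 'Seizure' and 'Confusion or change in alertness' to Appendix T as prompted items. Use the same prompted list at V2, V3 and the 30-day follow-up, with the recall period adapted to the interval: the past week at the calls, and the time since the last contact at the visits. Every dose is then asked about in the same terms, whether the contact is by telephone, telehealth or in clinic.

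The cost is a one-page form revision, seconds per contact and slightly higher recorded event counts. A common list does not remove the difference in recall length between weekly calls and the single fixed-dose contact, so the report should state that difference beside the dose comparison.
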